2.2 Study Rationale

This is a Phase 2, double-blind study in patients with erosive esophagitis due to GERD LA grades C or D, and in patients with at least partial symptom response but still endoscopically unhealed (LA grades A or B) after 8 weeks history of standard treatment healing course with PPI, designed to support dose selection for Phase 3. The pronounced acid control of X842 is assumed to provide high endoscopic healing rates already after 4 weeks treatment course. The four dose levels of X842 are selected based on data from the Phase 1 studies where the 50 mg BID dose displayed an acid control slightly stronger than observed for standard PPI. The dose selection for Phase 3 will be based on the proportion of endoscopic healing following each dose of X842, the respective safety data and the PK profile. Lansoprazole will serve as an active comparator.

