4.10.1.6 Examination of Subgroups

The uniformity of the treatment effect for the primary efficacy variable will be examined for the following subgroups:

1. Age (<60 years, \geq 60 years)
2. Sex (Male, Female)
3. Erosive esophagitis due to GERD LA grade C or D, erosive esophagitis due to GERD LA grade A or B who are partial responders to PPI treatment.

Summaries of the primary efficacy variable by treatment group and subgroup will be produced.

Summaries of the secondary endpoints Percentage of heartburn-free 24-hour days during the Weeks 1-8 based on eDiary (mRESQ-eD) and Percentage of 24-hour days with at most mild heartburn symptoms during the Weeks 1-8 based on eDiary (mRESQ-eD) by treatment group and subgroup will also be produced.

Statistical modeling of dose-response will be performed on subgroups defined by LA grade. No formal statistical analysis will be performed within the other subgroups.

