- ED_{50} the dose that gives 50 percent of the maximum effect,
- h the Hill coefficient,
- δ the rate of change for the logistic and exponential models,
- β is the slope for linear model,
- E_0 the basal effect at $d = 0$ and
- E_1 the scale parameter in the exponential model.

In the MCP-Mod approach, all statistically significant models listed above will be averaged in order to estimate the median dose for a given targeted response via inverse prediction along with associated 95% intervals using a bootstrap re-sampling method.

For the contrast test the following guesstimates will be assumed.

Model	Guesstimate
Emax	ED50 = 50
SigEmax1	ED50 = 50
Logistic, Exponential	$\delta = 200$

This MCP-Mod analysis will be performed using the R software (“DoseFinding” and “ggplot2” packages) [5], as follows:

1. MCP step:
 - a. Logistic regression model on the response variable with dose levels as categorical to obtain coefficients estimate and the relative covariance matrix.
 - b. “Mod” function of the “DoseFinding” package to perform the multiple contrast test (function “MCTtest”) part on the pre-specified candidate models
 - c. Significant candidate models will be evaluated by t-Test statistic and the adjusted p-value. Candidates for the modeling part will be selected with the following criteria:
 - i. Take the most significant candidate model ($p < 0.05$) or models if the t-Test statistic is equal.
 - ii. Stop if any of the model has not signal ($p > 0.05$).
2. Modeling step (Bootstrap):
 - a. $N = 1,000$ bootstrap samples of dose responses will be generated by a multivariate normal distribution with vector mean equal to the logit coefficients estimated on the MCP step and covariance matrix as its coefficients related covariance matrix.
 - b. For each Sample:
 - i. Fit the model by the “fitMod” function and select the best with goodness of fit based on the AIC criteria.
 - ii. Prediction of response probabilities based on the best model.
 - iii. Save the predicted values.
3. Compute the median of the bootstrap predicted values and 95% CIs.
4. Extraction of the dose at the target response probability with 95% CI.

Should there be three or more candidate model fail to fit on a bootstrap sample, the estimate for the bootstrap sample will be taken as unreliable. In case less than 70% of bootstrap sample estimates are taken as reliable an additional generalized linear mixed model (GLMM) analysis will be performed as

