follows. A regression model with treatment (including Lansoprazole (QD) 30 mg group) and GERD category (with levels of A&B and C&D) as fixed and center as random effect will be fitted to binary data (logistic regression). Number of subjects with evaluable data and least squares mean estimates of response rates with accompanying 90% CIs will be provided for each dose level and for Lansoprazole (QD) 30 mg group using model estimates of the GLM described above.

The following summaries will be provided by study treatment group based on central reading results where some descriptive summaries on FAS will be presented on both subgroups of erosive and non-erosive patients at screening according to central reading. A subgroup analysis based on the LA grade A/B patients by prior PPI treatment will also be presented since some of the LA grade A/B patients were originally LA grade C/D patients as assessed by the investigator.

- Percentage of patients with esophageal mucosa healing after 4 weeks (FAS erosive/non-erosive/PPS)
- Percentage of patients with esophageal mucosa healing after 4 weeks by LA Grade (FAS subgroup of erosive patients/PPS)
- Percentage of patients with esophageal mucosa healing after 4 weeks by age (FAS subgroup of erosive patients /PPS)
- Percentage of patients with esophageal mucosa healing after 4 weeks by sex (FAS subgroup of erosive patients /PPS)
- Percentage of patients with esophageal mucosa healing after 4 weeks by center (FAS subgroup of erosive patients /PPS)
- Percentage of patients with esophageal mucosa healing after 4 weeks by H.Pylori at Baseline (FAS erosive/non erosive /PPS)
- Percentage of patients with esophageal mucosa healing after 4 weeks by Prior PPI Treatment (FAS Patients with LA Grade A/B)
- Bar-charts of percentage of patients with esophageal mucosa healing after 4 weeks (FAS erosive/non erosive /PPS)
- Bar-charts of percentage of patients with esophageal mucosa healing after 4 weeks by LA Grade (FAS subgroup of erosive patients /PPS)
- MCP-MOD: Testing a dose-response signal for Response Rate (FAS subgroup of erosive patients /PPS)
- Figure for dose-response shapes based on model-averaging method over all models in the candidate set (FAS subgroup of erosive patients /PPS)
- Results of the contrast test from the MCP-Mod analysis (FAS subgroup of erosive patients /PPS)
- Model parameter estimates of the individual dose-response models (FAS subgroup of erosive patients /PPS)

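### Ordinary logistic regression in MCP step 1a gives a dose at which every patient heals almost no weight in the dose-response analysis; the exposure lies mainly in the PPS and LA-grade models, and is small in the primary FAS erosive analysis

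*SAP*

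**What the plan says.** SAP 4.10.2 sets out the primary dose-response analysis in steps. Step 1a is a "Logistic regression model on the response variable with dose levels as categorical to obtain coefficients estimate and the relative covariance matrix". The later steps use those estimates and that matrix. Step 1b is the multiple contrast test. In step 2a, "bootstrap samples of dose responses will be generated by a multivariate normal distribution with vector mean equal to the logit coefficients estimated" in the MCP step, with the "covariance matrix as its coefficients related covariance matrix". Step 2b fits the candidate curves to each sample, and steps 3 and 4 read off the dose predicted to heal 85%. Step 1c stops the procedure when no candidate shape reaches p < 0.05.

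Neither the SAP nor the readable part of its amendment names a penalised, exact or bias-reduced estimator, or a rule for a dose with 0% or 100% healing. The one safeguard in 4.10.2 counts bootstrap samples in which three or more candidate models fail to fit.

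Three other places bear on the point:
- SAP 4.10.1.6: "Statistical modeling of dose-response will be performed on subgroups defined by LA grade". SAP amendment 4.3.3 also lists A/B and C/D dose-response models on the PPS.
- SAP 4.10.1.3: in the primary analysis a missing healing result counts as not healed.
- Protocol 2.2: the acid control of X842 "is assumed to provide high endoscopic healing rates already after 4 weeks treatment course". No planning rate is readable, because Protocol 9.2 and SAP 4.12 are redacted.

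**The concern.** A log-odds has no finite maximum-likelihood estimate when all patients in a group respond. Software stops at some large value with a huge standard error. Methods that weight by the inverse covariance then treat the dose as if it carried no information, although it is the strongest evidence in the data set. The most favourable outcome for a dose can therefore weaken the test for a dose-response signal, trigger the stop in step 1c, or leave the 85% dose to be read from the other arms alone. The reliability rule need not react, because the curves can still be fitted. If the team chose a repair after seeing such a result, that choice would be data-driven.

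**Working it through.** The plan gives no figure to reproduce on this point. The inputs are 48 patients per arm (240 in five arms), 200 evaluable, so 40 per arm and one sixth non-evaluable (Protocol 1.1), and an approximately 50:50 LA split (Protocol 6.3.1), so 24 randomised or 20 evaluable per dose in each LA stratum. Healing rates are assumptions.

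**1. What happens at a dose with 100% healing.** Take 20 per dose, no covariates. For x healed of n, the logit is b = ln(x/(n−x)) with variance v = 1/x + 1/(n−x). The optimal linear contrast has c_i ∝ (d_i − d_w)/v_i, where d_w is the mean dose weighted by 1/v, and z = Σc_i b_i / √(Σc_i² v_i).
- 14/17/20/20 healed: the fitted SE is 17,768 for both top doses, and their contrast weights are 0.000. Only two arms count: z = (1.735 − 0.847)/√(0.392 + 0.238) = 1.12, one-sided p = 0.13.
- 14/17/19/19 healed (two fewer): all arms count, z = 2.35, p = 0.009.
- 14/17/20/20 with Firth-type logits ln((x+0.5)/(n−x+0.5)) and variance 1/(x+0.5) + 1/(n−x+0.5): top-dose logits 3.71, SE 1.43, z = 2.54, p = 0.006.

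These are single-contrast values, not the plan's adjusted p-values.

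**2. Nearer to the plan's test.** Take 24 per dose and the SAP guesstimates. The logistic shape is left out because the SAP gives it no ED50. The SAP does not state sidedness; one-sided is assumed.
- 15/18/20/23 healed: max t 2.53, adjusted p = 0.008.
- 15/18/20/24 healed: 100 mg logit 18.6, SE 1,331, weight zero for every shape tested, max t 1.62, adjusted p = 0.061. Firth-type: max t 2.35, adjusted p = 0.013.
- For 15/18/20/24, the linear 85% dose is 79.9 mg with the 100 mg arm and 79.9 mg without it. The bootstrap with AIC selection (300 draws, a re-implementation) gave 80.5 mg both ways and chose the same model in 98% of draws. Its lower bound at 100 mg was 0.59, against a Clopper-Pearson lower limit of 0.858 for 24/24.
- R's glm reported convergence without a warning; other packages may print a separation warning.

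**3. How likely is it?** With true healing p_i, n per dose and a share m missing and counted as not healed, P(at least one dose at 100%) = 1 − Π(1 − [p_i(1−m)]^n). For 80/85/90/93%, n = 20, m = 0: 1 − (0.9885 × 0.9612 × 0.8784 × 0.7658) = 36%.

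| Assumed healing, 25/50/75/100 mg | FAS, 48/dose, 1/6 missing | FAS, 48/dose, 5% missing | FAS LA subgroup, 24/dose, 1/6 missing | FAS LA subgroup, 24/dose, 5% missing | PPS, 40/dose | PPS LA subgroup, 20/dose |
|---|---|---|---|---|---|---|
| 85% at all | <0.001% | 0.01% | 0.1% | 2% | 0.6% | 15% |
| 80/85/90/93% | 0.001% | 0.3% | 0.4% | 8% | 7% | 36% |
| 90% at all | <0.001% | 0.2% | 0.4% | 9% | 6% | 40% |
| 85/90/95/97% | 0.005% | 2.7% | 1.1% | 24% | 40% | 75% |
| 95% at all | 0.005% | 2.9% | 1.5% | 30% | 42% | 83% |

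The PPS columns take m = 0, because the PPS is limited to completers (SAP 4.5). The FAS erosive will be somewhat smaller than 48 per dose, since centrally non-erosive patients leave it.

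**The case against.** The strongest reply is that the primary analysis is hardly exposed. One patient without a week-4 endoscopy counts as not healed and rules out a 100% dose in that arm. This stands, and it is why the FAS columns are small. The A/B and C/D models on the PPS are formally exploratory under SAP amendment 4.3.3, which also stands.

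The upper rows of the table are generous. Protocol 4.3 picks 25 mg to be no better than lansoprazole in a harder-to-treat population, so 90% or 95% healing at every dose is not the planned picture.

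Nor does the 100% rate disappear from the report. SAP 4.10.2 gives each dose's rate with a Clopper-Pearson interval, and Protocol 2.2 bases dose selection on healing, safety and PK together.

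A reader might also infer that the GLMM fallback, or a centre in which everyone heals, discards a dose. The documents do not support either. The fallback reports response rates and intervals per dose, with no contrast or 85%-dose step, so a 100% arm would at most get an uninformative interval. When one of four centres healed completely in a trial fit, the dose contrasts (z = 3.876) matched those with that centre removed; no dose dropped out.

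Zero weight in the curve fits depends on covariance weighting, which SAP reference [3] implies but the SAP does not state. The DoseFinding package itself was not run.

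**Conclusion.** The point holds as a robustness gap that should be fixed. If a dose reaches 100% healing, step 1a gives it essentially no weight in the contrast test and, under covariance-weighted fits, practically none in the bootstrap and the 85% dose. Nothing in the plan is designed to catch this.

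Its size depends on the analysis set and on assumed healing. It is small in the FAS erosive primary analysis, and 0.1% to 1.5% (one sixth missing) or 2% to 30% (5% missing) in FAS LA subgroups. It is material in the completer-based PPS, above all in its A/B and C/D models, at about 15% to 36% in the two more moderate scenarios. A reader might infer that the primary dose estimate is likely to be lost; the non-responder rule in SAP 4.10.1.3 does not support that.

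**What to change.** In step 1a, for the FAS erosive, PPS and LA-grade models, replace ordinary logistic regression with Firth bias-reduced logistic regression using the same covariates, and pass its estimates and covariance to the contrast test, the bootstrap and fitMod. At minimum, pre-specify this whenever a dose shows 0% or 100% healing.

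The cost is one sentence in the SAP, one changed function call and slight shrinkage: 36/40 = 90.0% becomes 36.5/41 = 89.0%. Where no dose is at 100%, little need change: for 15/18/20/23 of 24 the linear-contrast z is 2.50 by maximum likelihood and 2.51 with Firth-type estimates. SAP amendment section 3 says that it was written after unblinding, so a change adopted now should be labelled as not pre-specified.

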- Estimation of potential target dose based on model-averaging method over all models in the candidate set (FAS subgroup of erosive patients /PPS)

A sensitivity analysis based on local readings will be provided by study treatment group:

- Percentage of patients with esophageal mucosa healing after 4 weeks (Investigator or Endoscopy specialist reading) (FAS)
- Percentage of patients with esophageal mucosa healing after 4 weeks by LA Grade (Investigator or Endoscopy specialist reading) (FAS)

A second sensitivity analysis based on local readings and how those local readings were reclassified by central reading will be provided by study treatment group.

There will be 6 categories:

- Grade C/D that stayed C/D
- Grade C/D reclassified as A/B
- Grade C/D reclassified as grade 0 (non erosive) – if any
- Grade A/B reclassified as C/D – if any
- Grade A/B that stayed A/B
- Grade A/B reclassified as grade 0 (non erosive)

- Percentage of patients with esophageal mucosa healing after 4 weeks by Investigator LA Grade and its reclassification (FAS)

A listing of upper endoscopy results will be provided.

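### SAP 4.10.2 prints incompatible rules for which models give the primary 85%-healing dose, and its stop rule as worded contradicts its own averaging rule

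*SAP*

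**What the plan says.** The aim in SAP 4.10.2 is the dose giving 85% healing at 4 weeks, and SAP 4.10.1 wants it estimated with good precision. The documents name its source in these ways:

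- Protocol 9.4.7 and the first part of SAP 4.10.2: the single best-fitting model.
- SAP 4.10.2, MCP-Mod introduction: "all statistically significant models listed above will be averaged in order to estimate the median dose for a given targeted response".
- SAP 4.10.2, step 1c(i): "Take the most significant candidate model", with the extension "or models if the t-Test statistic is equal".
- SAP 4.10.2, step 2b(i), in each of 1,000 bootstrap samples: fit, then "select the best with goodness of fit based on the AIC criteria". Steps 3 and 4 take the median and 95% interval of the predictions and read off the dose.
- SAP 4.10.2, output list: "Figure for dose-response shapes based on model-averaging method over all models in the candidate set" and "Estimation of potential target dose based on model-averaging method over all models in the candidate set".

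Two further rules act on the models carried forward. Step 1c(ii) reads "Stop if any of the model has not signal", with p > 0.05. A bootstrap sample is unreliable if "three or more candidate model fail to fit on a bootstrap sample", and a mixed-model analysis is added when fewer than 70% of samples are reliable. The sidedness of p < 0.05 is not stated.

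Section 1 of the SAP amendment keeps the original SAP unless it says otherwise. Its readable primary section (4.5.2) names the analysis set and says nothing on model choice.

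**The concern.** A programmer following this section must decide whether one model, the significant models or all five produce the primary estimate, and whether one failed contrast ends the modelling. Each choice has a printed sentence behind it. The reported point estimate, and in some trials whether any modelled dose is reported, therefore depends on which sentence is followed. Section 3 of the SAP amendment says it was written after unblinding, so a choice made now without explanation is open to the suspicion that it followed the results.

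**Working it through.** The documents give no figure to reproduce, because the sample-size text (Protocol 9.2, SAP 4.12) is redacted. The text comes first, then an illustration under assumed healing rates.

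**1. Models behind the dose under each rule**

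| Rule | Models used |
|---|---|
| Best-fitting model | one, chosen by fit |
| MCP-Mod introduction | all with p < 0.05 |
| Step 1c(i) | one, chosen by contrast t statistic; more only on a tie |
| Step 2b(i) | lowest AIC per sample; needs at least two to choose between |
| Output list | all five, no significance filter |

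Step 2b followed by the median is a bootstrap form of model averaging. It is also a best-fit rule within each sample, so it can be reconciled with either description. Step 1c(i) cannot. If it leaves one model, AIC has nothing to choose between. Three candidate models cannot fail when one or two are fitted, so the mixed-model fallback cannot be triggered.

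**2. Ties.** As printed, the Logistic curve is E0 + Emax/exp((ED50 − d)/δ), with no 1 + in the denominator. This equals E0 + [Emax·exp(−ED50/δ)]·exp(d/δ), which is the Exponential curve. Both have guesstimate δ = 200, so their t statistics are identical. In simulated trials with a signal, the pair ties as most significant in roughly 10 to 50%, depending on the scenario. The two curves coincide, so AIC still has no real choice.

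**3. Stop rule.** Read literally, modelling continues only if all five contrasts are significant. Choosing among models, or averaging the significant ones, would then have nothing to filter. The coherent reading is to stop if no model is significant.

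**4. Worked example.** Assumed: 36, 41, 42 and 43 healed of 48 at 25, 50, 75 and 100 mg BID, no covariates, standard Logistic formula with assumed ED50 = 50.

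- Logits ln(x/(48 − x)): 1.099, 1.768, 1.946, 2.152. Variances 1/x + 1/(48 − x): 0.111, 0.167, 0.190, 0.223. Target: ln(0.85/0.15) = 1.735.
- Contrast t statistics: Emax 2.08, SigEmax 2.07, Logistic 1.99, Linear 1.99, Exponential 1.96 (1.96 also for the Logistic as printed). One-sided adjusted p runs from 0.024 (Emax) to 0.032 (Exponential).
- Linear, weighted least squares: 0.841 + 0.0143d. AIC = χ² + 2k = 0.43 + 4 = 4.4. Dose = (1.735 − 0.841)/0.0143 = 62.5 mg.
- Emax fit: −5.80 + 8.33d/(5.19 + d). AIC = 0.02 + 6 = 6.0. Dose about 49 mg.
- Best-fitting model (Linear): 62.5 mg. Most significant model (Emax): about 49 mg from its fit, 53 mg from its bootstrap. Lowest AIC per sample over all five: 59.5 mg. The upper 95% limit is not reached by 100 mg under either bootstrap.
- At one-sided 2.5% only Emax and SigEmax pass, SigEmax barely. The literal stop then gives no dose and the coherent reading continues, so sidedness matters too.

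Other assumed patterns: with 60/80/85/87% healed, the most significant model gives about 70 mg, the lowest AIC about 80 mg and an AIC-weighted average about 77 mg. With 65/75/82/88% all rules give about 88 mg.

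**5. Simulated trials with a signal** (five scenarios, 48 per arm, one-sided 5%, standard Logistic formula)

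| Comparison | Median difference | 10 mg or more |
|---|---|---|
| Most significant vs best-fitting single model | 3.5–7.5 mg | 7–31% |
| Most significant vs lowest AIC per sample over all five | 2.5–4 mg | 3–5% |
| All significant vs all five, lowest AIC per sample | 0 mg | 0–2% |

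The upper limit lies above 100 mg in 51–74% of trials (most significant) and 59–83% (all five).

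**6. Effect of the literal stop.** Percentage of trials with no modelled dose, 48 per arm, one-sided 5%:

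| True healing rates | Stop if none significant | Literal | Added |
|---|---|---|---|
| 70/78/85/90 | 18 | 27 | 9 |
| 75/82/86/90 | 40 | 49 | 9 |
| 80/85/88/90 | 62 | 71 | 9 |
| 70/88/89/90 | 15 | 22 | 7 |

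Repeat simulations put the added share at 7 to 10 points.

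**The case against.** The strongest reply is that a sensible reading exists. Step 2b is a recognised way to average over models, and it fits both best fit and averaging. The literal stop rule defeats the sentences around it, and the output list speaks of testing a dose-response signal, which points to one overall test. On that view this is poor wording that any competent programmer would read correctly, and the sidedness may be set in the MCTtest code. The shifts are also small beside doses spaced 25 mg apart, and the 62.5 against 49 mg example is larger than the typical simulated difference.

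Much of this stands. The literal stop is a wording fault with one coherent correction, the shifts are usually modest, and averaging the significant models against using all five is nearly a distinction without a difference in size. The reply does not rescue step 1c(i), which is clear in its wording and incompatible with the steps that follow it.

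Three stronger inferences are tempting and not supported:

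- That the conflict leaves 15 to 62% of trials without a modelled dose. Those rates come from requiring a signal at all; only the added 7 to 10 points come from the wording.
- That the conflict destroys precision. The interval is wide under either bootstrap.
- That the rule was chosen after seeing results. The documents show the timing of the amendment, not such a choice.

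**Conclusion.** The point holds on the text. The printed rules cannot all govern the primary dose, and following steps 1c(i) and 1c(ii) as written gives a different dose or none. It should be fixed, but its reach is limited: it concerns the point estimate and its credibility, and Protocol 2.2 makes Phase 3 dose selection depend also on healing per dose, safety and PK.

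The sizes rest on assumed healing rates, 48 per arm and mostly a one-sided 5% test. The primary set is FAS erosive, whose size is not visible. With 40 per arm, or at one-sided 2.5%, the literal stop adds 7 to 11 points; with LA grade and four assumed centers in the model, 5 to 10. The missing term in the Logistic formula may be a fault of text extraction, and the main conflict does not depend on it. Redacted parts of the SAP amendment (among them 4.5.4 and 4.5.5.1) could not be checked. The mg figures illustrate the rules and say nothing about which dose is right.

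**What to change.** 1. Delete the most-significant-model rule in step 1c(i). State one model set and one estimator. For example: once at least one contrast is significant, fit every model in the stated set in each bootstrap sample, use the one with the lowest AIC, and read the dose and 95% interval from the median and percentiles of the predictions.
2. Amend the best-fitting-model text, the MCP-Mod introduction and the output list in SAP 4.10.2 to match, and say explicitly whether the significance filter is kept or dropped.
3. Reword step 1c(ii) to stop if no model is significant, and state the sidedness of p < 0.05.
4. Correct or confirm the Logistic formula.
5. Because the amendment post-dates unblinding, label the choice post hoc and report the target dose under each printed rule as a sensitivity analysis.

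The cost is SAP wording and a rerun of existing code, with no new data. The choice remains post hoc, which the sensitivity analysis discloses but cannot undo. No change to the signal requirement itself is asked for.

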9.4.7 Efficacy Analyses

Analyses of the primary efficacy endpoint will be performed for both the FAS and PPS; analyses of the secondary and exploratory efficacy endpoints will be performed for the FAS only.

Endpoint	Statistical Analysis Methods
Primary	
Analysis of primary endpoints will focus on the rate of esophageal mucosa healing in the four X842 dose groups to identify the dose that will lead to having 85% of the patients have esophageal mucosa healing after 4 weeks of treatment. It will involve dose-response modeling, evaluating a sequence of dose-response models for the healing rate including the Linear, Exponential, E_{max}, Sigmoid E_{max} and Logistic models (on logit scale). The models will be compared in terms of model fit, and the target dose estimated as the dose providing the target effect of 85% healing rate from the best fitting model will be derived. The data will be summarized and analyzed descriptively by treatment utilizing statistical summary tables and plots.

Secondary	
The data will be summarized and analyzed descriptively by treatment utilizing statistical summary tables and plots for the below secondary efficacy endpoints:
 
1. Percentage of heartburn-free 24-hour days during the Weeks 1-8 (Visits 2-9) based on eDiary (RESQ-eDiary), including splits into day- and nighttime evaluations.2. Percentage of 24-hour days with at most mild heartburn symptoms during the Weeks 1-8 (Visits 2-9) based on eDiary (RESQ-eDiary), including splits into day- and nighttime evaluations.3. Investigator assessment of symptom at Weeks 1-8 (Visits 2-9)4. Reflux related symptoms as measured by change from baseline in QOLRAD score assessed after 1, 2, 4 and 8 weeks of treatment

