4.10.1.4 Multiple Comparisons/Multiplicity

No formal statistical testing is planned. Hence no adjustments for multiplicity are required.

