4.10.2 Primary Efficacy Variable(s)

Upper endoscopy for the examination of esophagus will be performed to confirm patient eligibility as well as the primary endpoint. The endoscopy examinations will be recorded on a video shot/digital images and these endoscopy videos/digital images will be evaluated by Investigator or endoscopy specialist, as required. Grade of erosive esophagitis due to GERD will be determined by the appropriately trained Investigator or endoscopist according to the LA classification (see Appendix 8 of protocol).

The endoscopy videos/digital images will be collected into a central database, with the appropriate anonymization. All videos and digital images will be centrally reviewed retrospectively. This review will include reassessment of the LA grading and other findings which may constitute exclusion criterion. The central reading evaluation will override the investigators' evaluations and will be used for all reporting and modelling. In case central reading evaluation is missing for a patient at screening or at week 4, due to poor video quality for example, the investigators' evaluations will replace the missing central reading. Hereafter, analyses based on central reading will consider central readings with imputations of local readings if missing.

Data obtained from patients deemed to have been ineligible for study enrollment following the retrospective analysis will be excluded from the per protocol analysis.

In the FAS analysis, the following subgroups of patients will be evaluated:

- the subgroup of patients classified as erosive with grade A/B or C/D at screening according to central reading
- the subgroup of patients classified as non-erosive (grade 0) at screening according to central reading.

A sensitivity analysis will also be conducted to present the healing results based on investigator or endoscopy specialist assessments (local reading). A second sensitivity analysis will be presented by category of LA Grade as assessed by the investigator and reclassified by central reading.

The primary objective of the study is to support dose selection for X842, through assessment of healing of erosive esophagitis due to GERD based on endoscopic assessment after 4 weeks of treatment. The aim is to identify the dose that will lead to having 85% of the patients have esophageal mucosa healing after 4 weeks of treatment.

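### The model-based 85%-healing dose depends on a contrast test at p < 0.05, which conflicts with other parts of the plan, and the GLMM fallback does not cover a failed test

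*SAP*

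**What the plan says.** **Aim.** SAP 4.10.2: "The aim is to identify the dose that will lead to having 85% of the patients have esophageal mucosa healing after 4 weeks of treatment".

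**Rule without a test.** Protocol 9.4.7 compares five dose-response models on fit, and "the target dose estimated as the dose providing the target effect of 85% healing rate from the best fitting model will be derived". SAP 4.10.2 repeats this before it introduces MCP-Mod. SAP 4.10.1.4 adds: "No formal statistical testing is planned".

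**Rule with a test.** The MCP-Mod part of SAP 4.10.2 says that "all statistically significant models listed above will be averaged in order to estimate the median dose for a given targeted response". Its numbered steps are:

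1. Run the contrast test. "Take the most significant candidate model" with p < 0.05 (or models, if tied); "Stop if any of the model has not signal" (p > 0.05).
2. Draw 1,000 bootstrap samples and fit models to each.
3. Take the median and 95% interval of the predictions.
4. Extract the dose at the target response.

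**Output list.** The same section lists, without any condition, a target dose averaged over the whole candidate set.

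**Fallback.** A bootstrap sample is unreliable if three or more candidate models fail to fit. "In case less than 70% of bootstrap sample estimates are taken as reliable an additional generalized linear mixed model (GLMM) analysis will be performed". This GLMM gives a response rate with a 90% CI for each X842 dose and for lansoprazole, but no 85% dose.

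**Always reported.** Healing rate per arm with a 95% Clopper-Pearson CI.

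**The concern.** The question is one of estimation, yet one of the stated rules makes the estimate conditional on a significance test. A test of this kind fails most often when the curve across 25-100 mg is shallow. One way for that to happen is that the lower doses already heal well. The protocol allows for high rates: "The pronounced acid control of X842 is assumed to provide high endoscopic healing rates already after 4 weeks treatment course" (Protocol 2.2). There is no zero-dose arm to steepen the contrast.

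In that case the numbered steps would yield no 85% dose and no interval for it, and nothing says what replaces them. The GLMM, which could have supplied model-adjusted rates for each dose, would not be called. Because other parts of the plan state a different rule, whoever runs the analysis would have to choose between them, possibly with the data in view.

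**Working it through.** **1. Order of the steps.** Dose extraction is step 4 and the stop is in step 1. A stop in step 1 produces no bootstrap samples. The GLMM trigger is a percentage of bootstrap samples, so it cannot be met. This holds whether the stop rule means that no model is significant (the likely intention) or, literally, that at least one is not.

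**2. The statements side by side.**

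| Place | Which models give the 85% dose | Test required? |
|---|---|---|
| Protocol 9.4.7; SAP 4.10.2, opening text | Best-fitting model | No |
| SAP 4.10.2, MCP-Mod text | Average of all significant models | Yes |
| SAP 4.10.2, step 1c | Most significant model(s) | Yes, otherwise stop |
| SAP 4.10.2, output list | Average over all candidates | None stated |

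The SAP amendment keeps the SAP unless it says otherwise, and its readable text changes none of these. Parts of it are redacted.

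**3. How often the test would stop the procedure.** The sample-size sections (Protocol 9.2, SAP 4.12) are redacted, so there is no power figure of the plan's own to reproduce and the healing rates below are assumptions.

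Inputs from the documents:
- Doses 25, 50, 75 and 100 mg.
- 240/5 = 48 randomized per arm and 200/5 = 40 evaluable per arm.
- The five candidate shapes, with ED50 = 50 (Emax, sigmoid Emax with h = 3.5) and δ = 200 (logistic, exponential).

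Further assumptions: logistic ED50 = 50 (not given), no center or LA-grade terms, and a stop only if no shape is significant.

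With observed logit L_i, weight w_i = n·p_i(1 − p_i) and shape values f_i, the contrast is c_i = w_i(f_i − f̄_w), where f̄_w is the w-weighted mean of f. The statistic is T = Σc_iL_i / √(Σc_i²/w_i). The procedure stops if the largest of the five T values does not exceed the multiplicity-adjusted critical value: 1.75 for one-sided 0.05, 2.07 for two-sided. The SAP does not state sidedness.

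*Hand check, linear shape, 70/80/85/90%, n = 40:*
- w = 8.4, 6.4, 5.1, 3.6; weighted mean dose = 1272.5/23.5 = 54.1.
- L = 0.847, 1.386, 1.735, 2.197.
- Σw(d − 54.1)L ≈ 303 and Σw(d − 54.1)² ≈ 17,030, so expected T ≈ 303/130.5 = 2.32.
- P(stop) ≈ Φ(1.75 − 2.32) = Φ(−0.57) ≈ 28%.

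*Simulation of all five shapes, one-sided 0.05:*

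| Assumed healing at 25/50/75/100 mg | Stop, 40 per arm | Stop, 48 per arm |
|---|---|---|
| 50/70/80/88% | about 1% | about 1% or less |
| 60/72/80/87% | 12% | 8% |
| 70/80/85/90% | 27% | 20% |
| 75/82/87/90% | 47% | 38% |
| 80/86/90/92% | 56% | 50% |
| 85/88/90/93% | 78% | 74% |

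Repeat runs agree to within about three points. Other settings raise the figures. For 70/80/85/90%, a two-sided test passes 59% and 69% of the time, so it stops 41% and 31%. The literal reading of the stop rule passes 63% and 72% (one-sided), so it stops 37% and 28%.

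**4. Would removing the test be enough?** No. Among stopped trials, an ungated linear-logit fit often puts the 85% dose outside 25-100 mg or has a slope that is not positive. This happens in roughly 30-55% of stopped trials across the four higher-healing rows, although one run put it near 70% for 85/88/90/93%. In the two steeper rows it is around 90% or more.

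**The case against.** **A signal test before modelling is part of the named method.** That is so, and the test is legitimate as a reported result. It does not explain why the protocol and the SAP's own opening text describe estimation without it, or why no outcome is defined when it fails. The statement in 4.10.1.4 could be read as concerning only comparisons with lansoprazole, but it is worded generally.

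**The test is only one of several stated rules.** This stands. The documents show an unresolved conflict, not a settled rule that the dose exists only if the test passes.

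**A reader might infer that the trial could end with no basis for choosing a dose.** The documents do not support that. Arm-level rates with Clopper-Pearson intervals are reported whatever the test shows, and Protocol 2.2 bases Phase 3 selection on healing per dose, safety and PK. What is lost is the model-based 85% dose and its interval.

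**A reader might also infer that a shallow curve near 85% is the likely outcome.** That is not supported either. Protocol 4.3 describes a harder-to-treat population, cites a clear Phase 1 dose response in acid control, and assumes 75 and 100 mg superior to lansoprazole. It expects 25 mg to heal at a rate lower than or similar to lansoprazole, but gives no rate. With a steep curve the test almost never stops the procedure.

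**The GLMM gives no 85% dose.** Correct. Triggering it supplies model-adjusted rates per dose and is only part of the remedy.

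**Conclusion.** The point holds in a limited form. One stated rule in SAP 4.10.2 can block the model-based estimate that the primary analysis exists to produce. That rule conflicts with Protocol 9.4.7 and with other text in the same SAP section, and the fallback cannot operate when it applies. The logic follows from the text and needs no assumed rates.

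The practical size does depend on them: about 1% for a steep curve, 20-27% for 70/80/85/90%, and about three in four for 85/88/90/93%. These figures rest on assumed healing rates, a one-sided adjusted test, no covariates and 40 to 48 per arm. Redacted text in the SAP amendment could alter the rule, which cannot be checked.

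**What to change.** In SAP 4.10.2:

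1. Reconcile the opening text, the MCP-Mod steps and the output list into one rule. Report the contrast test, but estimate the dose-response curve and the 85% dose with its interval whatever the test shows. Say which models enter: the best-fitting one or the average, and over which set.
2. State what is reported when the estimated 85% dose falls outside 25-100 mg or the slope is not positive: target met at or below the lowest tested dose, or not reached by the highest.
3. Add the absence of any significant candidate model as a second trigger for the GLMM. Report model-estimated healing with a CI for each tested dose and which tested doses reach 85%.

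The cost is a short text edit plus changes to the target-dose outputs; the GLMM is already specified. With a shallow curve the dose interval will be wide or unbounded and must be shown as such. The SAP amendment was written after unblinding and records that healing results had already been communicated, so any change made now must be labelled post hoc.
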